3.1 Inclusion Criteria

- 1. Histologically confirmed Diffuse Large B-cell Lymphoma (DLBCL) or transformed DLBCL
- 2. Disease status defined as:
 - a. Patients with relapsed or refractory DLBCL that has relapsed post-transplant or that has been determined to be ineligible or unsuitable for transplant. Patients must have received at least one prior systemic therapy.
- 3. Patients must have measurable (≥ 1.5 cm) or evaluable disease. Baseline measurements and evaluations must be obtained within 21 days of registration to the study. Abnormal PET scans will not constitute evaluable disease, unless verified by CT scan or other appropriate imaging. Measurable disease must have at least one objective measurable disease parameter. A clearly defined, bi-dimensionally measurable defect or mass measuring at least 1.5 cm in diameter on a CT scan will constitute measurable disease. Proof of lymphoma in the liver is required by a confirmation biopsy. Skin lesions can be used as measurable disease provided bi-dimensional measurements are possible.
- 4. Adequate organ system function, defined as follows:
 - a. Absolute neutrophil count (ANC) $\geq 1.0 \times 10^9$ /L
 - i. By automated or manual review, whichever is greatest
 - b. Platelets $\geq 100 \times 10^9$ /L:
 - i. Unless due to bone marrow infiltration then eligible if platelets > 50 x 10⁹/L)
 - c. Total bilirubin \leq 1.5 x upper normal limit if documented hepatic involvement with lymphoma, or \leq 5 x upper normal limit if history of Gilbert's Disease.
 - d. Alanine aminotransferase (ALT) and aspartate aminotransferase (AST) ≤2.5 x ULN if no liver involvement or ≤5 x the ULN if documented liver involvement
 - e. Creatinine ≤2.0 mg/dL OR calculated creatinine clearance ≥50 mL/min (as calculated by the Cockcroft-Gault method, Appendix B)
- 5. ECOG performance status ≤2 or expected survival duration of > 2 months (Appendix C)
- 6. Patients must be ≥19 years of age (the age of consent in Nebraska)
- 7. Ability to swallow and retain oral medication
- 8. Women must not be pregnant or breast-feeding due to teratogenic effects of therapy.
 - a. All female patients of child-bearing potential must have a negative serum pregnancy test within 2 weeks prior to treatment to rule out pregnancy
 - b. Pregnancy testing is not required for post-menopausal or surgically sterilized women.

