3.2 Exclusion Criteria

- 1. Currently receiving cancer therapy (i.e., chemotherapy, radiation therapy, immunotherapy, biologic therapy, hormonal therapy, and surgery and/or tumor embolization) or any investigational drug within 7 days of Cycle 1/Day 1, 14 days of Cycle 1/Day 1 for limited palliative radiation, and/or five half-live of an oral therapy.
 - a. Corticosteroid therapy started at least 7 days prior to initiation of treatment (prednisone ≤10 mg daily or equivalent) is allowed as clinically warranted). Topical or inhaled corticosteroids are permitted.
- 2. Major surgery or a wound that has not fully healed within 4 weeks of enrollment.
- 3. History of stroke or intracranial hemorrhage within 6 months prior to enrollment.
- 4. Requires anticoagulation with warfarin or equivalent vitamin K antagonists (eg, phenprocoumon.
- 5. Vaccinated with live, attenuated vaccines within 4 weeks of enrollment.
- 6. Autologous hematologic stem cell transplant within 3 months of study entry.
- 7. Allogeneic hematologic stem cell transplant within 12 months of study entry.
- 8. Active graft versus-host disease and must not be on immunosuppression.
- 9. Wide field radiotherapy within 28 days of Cycle 1/Day 1 or active side effects of such therapy
- 10. Active Hepatitis B (HBV) or C (HCV) infection (negative serology required excluding those with are seropositive due to prior vaccination) and/or known history of human immunodeficiency virus (HIV)
- 11. Primary central nervous system involvement only
- 12. Require treatment with strong CYP3A inhibitors
- 13. Known history of drug-induced liver injury, alcoholic liver disease, primary biliary cirrhosis, ongoing extra-hepatic obstruction caused by stones, cirrhosis of the liver or portal hypertension
- 14. Any life-threatening illness, severe and/or uncontrolled medical condition, or organ system dysfunction, laboratory abnormality, psychiatric illness or other condition which, in the Investigator's opinion, could compromise the subject's safety, interfere with the absorption or metabolism of ibrutinib capsules, put the study outcomes at undue risk or affect their participation in the study such as:
 - a. Symptomatic, or history of documented congestive heart failure New York Heart Association (NYHA) functional classification III-IV (NYHA, Appendix D)
 - b. QTc >470 msec (unless related to pacemaker) on EKG within 21 days of initiation of treatment
 - c. Angina not well-controlled by medication

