5.1 Pre-treatment Evaluations Standard of Care (SOC)

Within 21 days prior to the Date of Enrollment, date of the start of study treatment / first study related intervention (unless otherwise specified below). No tests or procedures are conducted solely for the purposes of research to determine subject eligibility.

- History and physical
- Informed Consent
- CBC, diff, platelets, CMET, LDH
- Hepatitis B (HBV) or C (HCV) serology
- Serum pregnancy test (if applicable) within 14 days of first study-related treatment date.
- Height and weight
- Vital signs, including blood pressure
- Performance Status
- EKG
- PET/CT baseline radiologic evaluation; NOTE for f/u if a Deauville 3 (CR) is achieved then CT chest, abdomen and pelvis with contrast may be used. Further PET/CT scans are optional at the investigators discretion.
- Mandatory research peripheral blood (20 mL) for cell free DNA assessment and T-cell characterization will be collected in an EDTA tube pretreatment (day of biopsy or initiation of treatment), day 8, 1 month (+/- 3 days) and 10mL at subsequent radiographic response assessments, after cycle 2, 4, 6, 9, and 12. (+/- 7 days). After Month 12, efficacy assessments should occur at the investigators discretion with collection of a research blood sample only if feasible. Should the patient consent any leftover peripheral blood collected for research will be stored at UNMC for future IHC and DNA unspecified research use.
- Optional Research Samples (Appendix G):
 - Should the patient consent, 3 additional optional lymph node biopsies for molecular profiling will be obtained at days 0 (pre-treatment; core biopsy), day 8 (FNA) and end of treatment (progressive disease, toxicity, or end of study—1 year; core biopsy) to evaluate the baseline characteristics and dynamic shifts in mutational landscape, transcriptional signatures and intracellular signaling cascades in primary tumor cells as well as assessment of comparative serologic response to radiographic assessments of response.

Specimens submitted, by patients who consent to the additional specimen collection, will be processed to maximize their utility for future unspecified research projects and may include, but not limited to, extraction of plasma, serum, DNA and RNA. Specimens will be archived with appropriate safeguards to ensure an efficient system for the prompt linkage and retrieval of the stored samples with the subject's study records.

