5.2.2 Guidelines for Administration of Ibrutinib

- Method of Administration: Ibrutinib 4 capsules each 140mg = 560mg will be administered orally once daily.
 Ibrutinib should be taken in the evening. (NOTE: After cycle 2 if no CTE have been seen then the patient can have the option to take umbralisib and Ibrutinib dosing together at the same time of day).
- Ibrutinib capsules should be swallowed whole with a full glass (approximately 8 ounces) of water. Ibrutinib capsules should not be opened, chewed or dissolved.
- Potential Drug Interactions: Avoid co-administration with strong or moderate CYP3A inhibitors and consider
 alternative agents with less CYP3A inhibition. Concomitant use of strong CYP3A inhibitors which would be
 taken chronically (e.g., ritonavir, indinavir, nelfinavir, saquinavir, boceprevir, telaprevir, nefazodone) is not
 recommended. For short-term use (treatment for 7 days or less) of strong CYP3A inhibitors (e.g., antifungals

and antibiotics) consider interrupting ibrutinib therapy until the CYP3A inhibitor is no longer needed [see Drug Interactions (7.1)]. Reduce ibrutinib dose to 140 mg if a moderate CYP3A inhibitor must be used (e.g., fluconazole, darunavir, erythromycin, diltiazem, atazanavir, aprepitant, amprenavir, fosamprevir, crizotinib, imatinib, verapamil, and ciprofloxacin) [see Drug Interactions (7.1)]. Patients taking concomitant strong or moderate CYP3A inhibitors should be monitored more closely for signs of ibrutinib toxicity.

- Also avoid grapefruit and Seville oranges during treatment, as these contain moderate inhibitors of CYP3A and can alter ibrutinib pharmacokinetics.
- For patients with mild liver impairment (Child-Pugh class A), the recommended dose is 140 mg daily (one capsule). Avoid the use of ibrutinib in patients with moderate or severe hepatic impairment (Child-Pugh classes B and C) [see Use in Specific Populations (8.7) and Clinical Pharmacology (12.3)]
- Pre-medications: None

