5.6.1 Definitions of Cumulative Toxicity Event (CTE)

For this protocol, cumulative toxicity event (CTE) will be defined as follows: an adverse event attributed (definitely, probably or possibly related) to the study treatment and meeting following criteria within cycles 1 to 4. AE grading and assignment of attribution require documentation by medical personnel who are directly involved in the clinical care of protocol subjects.

Toxicity	Definition					
Hematologic	Either:					
	1. Grade 4 hematologic toxicities (attributed to either or both drugs) defined as:					
	b. Grade 4 thrombocytopenia (platelets < 25 K/μL)					
	c. Grade 4 neutropenia (absolute neutrophil count (ANC) < 0.5)					
	2. Grade 3 thrombocytopenia or neutropenia that results in a > 7 day delay in either					
	drug.					
Non-hematologic	Either:					
_	1. ≥ Grade 3 as per NCI Common Terminology Criteria for Adverse Events v4.03*					
	(attributed to either or both study drugs).					
	2. One week or greater delay in initiating any cycle day 1 due to continued drug-					
	related toxicity.					

^{*}Grade 3 nausea, vomiting, or diarrhea with maximal supportive treatment(s) will be considered a CTE. Fatigue Grade >/= 3 considered to be due to treatment (definitely, probably, or possibly related) will be considered a CTE.

Patients should be assessed clinically for toxicity at each visit using the NCI CTCAE v4.03 (http://evs.nci.nih.gov/ftp1/CTCAE/CTCAE) grading scale. The study will be terminated if a cumulative toxicity event (CTE) occurs in: ≥2/first 4; ≥4/first 8; or if more than 12 patients when the last (24th) evaluable patient has completed UNMC IRB#345-16 Protocol Version 4.2 Dated 07Oct2019

cycle 4. If a patient has progression of disease or is removed from study not related to a CTE after completion of 2 cycles but less than 4 cycles the patients safety evaluation will be included, but noted appropriately. If the patient receives less than 2 cycles than the patient will not be included and noted, but will not be replaced.

Dosing will occur only if a patient's clinical assessment and laboratory test values are acceptable.

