Appendix E Eligibility Checklist

Date Completed:	Institution:	Patient ID#:	Checklist Version #3.0 Dated: 14Jul2017
Evaluating the Safety and T Ibrutinib in Patients with Re	ngle-center Phase IIa Study Tolerability of umbralisib and lapsed or Refractory Diffuse A Trial of the Lymphoma Dry	Waiver #:	
Gender: []M []F	Race: [] White[] Black [] Native American [] Ot] Asian
Zip Code/country (if not USA):	' I Drimon, mothod at noumant intermetion:		
Inclusion Criteria: Respons	se should be YES		Yes No N/A
Histologically confirmed Diffuse Large B-cell Lymphoma (DLBCL) or transformed DLBCL		[] [] 1.	
2.			
 Disease status defined as Patients with relapsed or refractory DLBCL that has relapsed post-transplant or that has been determined to be ineligible or unsuitable for transplant. Patients must have received at least one prior systemic therapy. 			[] [] []
3. Patients must have measurable (≥ 1.5 cm) or evaluable disease. Baseline measurements and evaluations must be obtained within 21 days of registration to the study. Abnormal PET scans will not constitute evaluable disease, unless verified by CT scan or other appropriate imaging. Measurable disease must have at least one objective measurable disease parameter. A clearly defined, bi-dimensionally measurable defect or mass measuring at least 1.5 cm in diameter on a CT scan will constitute measurable disease. Proof of lymphoma in the liver is required by a confirmation biopsy. Skin lesions can be used as measurable disease provided bi-dimensional measurements are possible			[] []

4.	Adequate organ system function, defined as follows:	[]	[]	
	 a. Absolute neutrophil count (ANC) ≥ 1.0 x 10⁹/L i. By automated or manual review, whichever is greatest b. Platelets ≥100 x 10⁹/L: 			
	i. Unless due to bone marrow infiltration then eligible if platelets > 50 x 10 ⁹ /L)			
	c. Total bilirubin ≤ 1.5 x upper normal limit if documented hepatic involvement with lymphoma, or ≤ 5 x upper normal limit if history of Gilbert's Disease.			
	d. Alanine aminotransferase (ALT) and aspartate aminotransferase (AST) \leq 2.5 x ULN if no liver involvement or \leq 5 x the ULN if			
	documented liver involvement e. Creatinine ≤2.0 mg/dL OR calculated creatinine clearance ≥50 mL/min (as calculated by the Cockcroft-Gault method, Appendix B)			
5.	ECOG performance status ≤2 or expected survival duration of > 2 months (Appendix C)	[]	[]	
6.	Patients must be ≥19 years of age (the age of consent in Nebraska)	[]	[]	

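### Inclusion criterion 4c sets no bilirubin ceiling for patients with neither hepatic lymphoma nor Gilbert's disease, so as written it is stricter with liver involvement than without

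*Combined protocol and SAP*

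**What the plan says.** Section 3.1, item 4, defines adequate organ function. Line 4c limits total bilirubin to "1.5 x upper normal limit if documented hepatic involvement with lymphoma", or to 5 times the upper normal limit with a history of Gilbert's disease. Line 4d limits ALT and AST to 2.5 "x ULN if no liver involvement or ≤5 x the ULN if documented liver involvement". The Appendix E checklist, which may serve as the source document for eligibility, carries the same bilirubin line: "Total bilirubin ≤ 1.5 x upper normal limit if documented hepatic involvement with lymphoma".

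Other provisions bear on liver function:

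- Exclusion 10 covers active hepatitis B or C.
- Exclusion 13 covers named diagnoses: "Known history of drug-induced liver injury, alcoholic liver disease, primary biliary cirrhosis", and others.
- Inclusion 12 and exclusion 14 rest on the investigator's opinion. Exclusion 14 includes conditions that could "interfere with the absorption or metabolism of ibrutinib capsules".
- Section 5.2.2 advises: "For patients with mild liver impairment (Child-Pugh class A), the recommended dose is 140 mg daily (one capsule"). It says to avoid ibrutinib in classes B and C. Section 5.8 repeats this.
- Section 5.6.1 allows dosing only if the patient's "clinical assessment and laboratory test values are acceptable".

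**The concern.** Both limits in 4c depend on a condition, and no limit is given for a patient who meets neither. That is an odd place for a gap, because liver lymphoma is the usual reason to relax a hepatic limit, as 4d does. As written, 4c bars patients whose raised bilirubin has a documented lymphoma-related setting and sets no bar for patients whose raised bilirubin is unexplained.

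The consequence falls on the primary objective, safety and tolerability. Section 2.2.3 (Pharmacology/Toxicology) states that ibrutinib is metabolised in the liver, reports higher exposure in hepatic impairment, and notes that its safety there has not been evaluated. All three groups are assigned 560 mg. An attributed non-hematologic event of grade 3 or higher in cycles 1 to 4 is a CTE, and two patients with a CTE among the first four stop the trial. A single avoidable event in an over-exposed patient would be half of that early threshold.

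**Working it through.** No sample size or error rate is involved, so the check is a comparison of the rules.

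**Entry limits as written (multiples of the upper normal limit)**

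| Patient | Bilirubin (4c) | ALT/AST (4d) |
|---|---|---|
| Documented liver lymphoma | 1.5 | 5 |
| No liver lymphoma, Gilbert's disease | 5 | 2.5 |
| No liver lymphoma, no Gilbert's disease | none stated | 2.5 |

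Going from the third row to the first, the ALT/AST limit rises from 2.5 to 5, while the bilirubin rule goes from no stated limit to 1.5. The two lines run in opposite directions. For a patient with both liver lymphoma and Gilbert's disease, 4c does not say which limit governs.

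**Is it a transcription fault?** Section 3.1 and Appendix E carry the same condition in the same place, so a conversion error is unlikely.

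**Does another rule supply the number?** No.

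- Exclusions 10 and 13 turn on diagnoses.
- Inclusion 12 and exclusion 14 turn on opinion.
- 4d caps enzymes, not bilirubin.
- Section 5.6.1 does not define acceptable laboratory values.
- The screening bloods in section 5.1 ("CBC, diff, platelets, CMET, LDH") include a metabolic panel, but no stated bilirubin limit applies to the result for these patients.
- Child-Pugh class is not an eligibility criterion, and no Child-Pugh assessment is listed in section 5.1, the section 7.0 schedule or Appendix E.

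**Exposure, as background only.** Section 2.2.3 gives AUC increases of 2.7-, 8.2- and 9.8-fold for Child-Pugh A, B and C. If class A is recognised and the advised dose is given, the dose ratio is 140 / 560 = 0.25. Relative exposure is then 0.25 × 2.7 = 0.675, about 0.68 of the usual 560 mg exposure. If class A is not recognised and 560 mg is given, it is 2.7-fold. The 0.68 assumes AUC proportional to dose. The documents support that only roughly: mean AUC 953 / 680 = 1.40 for a dose ratio of 560 / 420 = 1.33. These ratios are by Child-Pugh class, not bilirubin, so they show why a limit matters and do not measure the effect of this gap.

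**The case against.** The strongest reply is that silence need not mean no limit. Item 4 purports to define adequate organ function, and in 4b and 4d a clinical condition relaxes a default. On that reading 4c lists two allowances from a default that was left out, a patient in neither category does not obviously pass, and nothing is inverted. This is a fair guess at intent, but the default is not in the text. Someone applying the checklist as written has no bilirubin number for these patients.

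The second reply is that few patients could slip through. Such a patient would need raised bilirubin with ALT and AST at or below 2.5 times the limit, no viral hepatitis and none of the liver diagnoses in exclusion 13, and the investigator would have to judge that exclusion 14 did not apply. The trial is single-center, eligibility questions go to the principal investigator, and chemistry is repeated through treatment. This stands, and it limits the likely number affected. It does not replace a stated limit with anything firmer than judgement.

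Third, the exposure ratios are not by bilirubin, and a ceiling would not by itself identify Child-Pugh A patients. A patient in that class with bilirubin at or below 1.5 times the limit would still enter and would still depend on someone recognising the class. Both points are correct. The correction closes the eligibility gap only.

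**Conclusion.** The concern holds. Section 3.1 and Appendix E state no bilirubin ceiling for patients with neither hepatic lymphoma nor Gilbert's disease, and read literally 4c is stricter with liver involvement than without, the reverse of 4d. Whether such a patient is excluded, given a reduced dose or started at 560 mg depends on investigator judgement or a known liver diagnosis.

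Confidence in the wording is high. The practical size is unknown: anywhere from 0 to 24 patients on the documents alone, with no CTE rate by bilirubin. The existing safeguards probably keep the number small, but that is a judgement, not a figure from the plan. No sample size, stopping boundary or analysis is affected. It should be corrected because the trial's primary question is safety.

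**What to change.** In section 3.1 (4c) and the matching line of Appendix E, make the 1.5 limit general and keep the Gilbert's allowance, for example: *Total bilirubin ≤ 1.5 x upper normal limit, or ≤ 5 x upper normal limit if history of Gilbert's Disease.* This uses only numbers already in the plan and also settles the case of a patient with both conditions. The documents do not establish what default was meant, so the sponsor-investigator should confirm 1.5. If a separate limit for documented hepatic involvement was intended, its value should be added as a further clause.

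The cost is one clause in two places, with no change to sample size, visit schedule or analysis.

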3.2 Exclusion Criteria

- 1. Currently receiving cancer therapy (i.e., chemotherapy, radiation therapy, immunotherapy, biologic therapy, hormonal therapy, and surgery and/or tumor embolization) or any investigational drug within 7 days of Cycle 1/Day 1, 14 days of Cycle 1/Day 1 for limited palliative radiation, and/or five half-live of an oral therapy.
 - a. Corticosteroid therapy started at least 7 days prior to initiation of treatment (prednisone ≤10 mg daily or equivalent) is allowed as clinically warranted). Topical or inhaled corticosteroids are permitted.
- 2. Major surgery or a wound that has not fully healed within 4 weeks of enrollment.
- 3. History of stroke or intracranial hemorrhage within 6 months prior to enrollment.
- 4. Requires anticoagulation with warfarin or equivalent vitamin K antagonists (eg, phenprocoumon.
- 5. Vaccinated with live, attenuated vaccines within 4 weeks of enrollment.
- 6. Autologous hematologic stem cell transplant within 3 months of study entry.
- 7. Allogeneic hematologic stem cell transplant within 12 months of study entry.
- 8. Active graft versus-host disease and must not be on immunosuppression.
- 9. Wide field radiotherapy within 28 days of Cycle 1/Day 1 or active side effects of such therapy
- 10. Active Hepatitis B (HBV) or C (HCV) infection (negative serology required excluding those with are seropositive due to prior vaccination) and/or known history of human immunodeficiency virus (HIV)
- 11. Primary central nervous system involvement only
- 12. Require treatment with strong CYP3A inhibitors
- 13. Known history of drug-induced liver injury, alcoholic liver disease, primary biliary cirrhosis, ongoing extra-hepatic obstruction caused by stones, cirrhosis of the liver or portal hypertension
- 14. Any life-threatening illness, severe and/or uncontrolled medical condition, or organ system dysfunction, laboratory abnormality, psychiatric illness or other condition which, in the Investigator's opinion, could compromise the subject's safety, interfere with the absorption or metabolism of ibrutinib capsules, put the study outcomes at undue risk or affect their participation in the study such as:
 - a. Symptomatic, or history of documented congestive heart failure New York Heart Association (NYHA) functional classification III-IV (NYHA, Appendix D)
 - b. QTc >470 msec (unless related to pacemaker) on EKG within 21 days of initiation of treatment
 - c. Angina not well-controlled by medication
 - d. Poorly controlled or clinically significant atherosclerotic vascular disease including cerebrovascular accident (CVA), transient ischemic attack (TIA), angioplasty, cardiac or vascular stenting within 6 months prior to enrollment
- 15. Prior malignancies within the past 1 years with exception of adequately treated basal cell, squamous cell skin cancer, or thyroid cancer; carcinoma in situ of the cervix or breast; prostate cancer of Gleason Grade 6 or less with stable PSA levels.
- 16. Women who are pregnant or breastfeeding. Women who agree to stop breastfeeding would be eligible
- 17. Known hypersensitivity to either study drug (umbralisib or Ibrutinib)

NOTE:

All questions regarding eligibility for **UNMC potential subjects** should be directed to the PI at [contact].

NOTE: The eligibility checklist (Appendix E) may be used as source documentation if it has been reviewed, signed, and dated prior to registration by the treating physician. The eligibility checklist must be accompanied by all other source documents that evidence the subject's eligibility (i.e., dictation, pathology, radiology, laboratory, etc.)

Page 14 of 65

Section 4.0 Registration Procedure:

All patients, with relapsed or refractory DLBCL that has relapsed post-transplant or that has been determined to be ineligible or unsuitable for transplant referred to The Nebraska Medical Center (TNMC), University of Nebraska Medical Center (UNMC), Bellevue Medical Center (BMC), and Village Point Cancer Center may be eligible for this trial.

Screening eligibility based on standard clinical care will be performed by the treating physician at the time of encounter. On initial presentation, a history and physical examination are performed, laboratory data obtained, and performance status is assessed. Imaging studies obtained include PET and a high-resolution multi-detector computed tomography (CT) of the chest, abdomen and pelvis. Further imaging studies will be obtained as clinically indicated. Pathology material must be reviewed, and a diagnosis of DLBCL confirmed by UNMC pathology department (retrospective). The patient's primary oncologist will make the decision as to screened eligibility of the candidate based on the eligibility criteria listed above, prior to offering consent.

If the patient is screened as potentially eligible, he/she will then be offered the option to participate. An informed consent will be signed by the patient after thorough review of the study is completed by the physician and his/her designee.

Some insurance carrier's may decline to cover the costs of usual medical care if the patient is participating in a clinical trial. The patient will be provided assistance by the research nurse coordinator or designated staff in determining if the insurance carrier will decline coverage. Insurance carriers may or may not pay for study related expenses. The patient can then decide if they wish to participate.

